8. STUDY POPULATION

8.1. Number of Subjects

In total, 70 subjects ages 2+ years and older will be enrolled in the study. Based on previous clinical data with comparable head lice products, a power analysis has been performed. Results indicated that a sample size of 35 subjects in each treatment group results in a power of 80%, considering a cure rate of 95% for

the test product and 55% for the reference product and a superiority margin of 15%. In case of dropouts, subjects will not be replaced.

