10.2. Data Analysis Considerations

Based on previous clinical data with comparable head lice products, a power analysis has been performed. In order to detect superiority (superiority margin of 15%) of the test product (cure rate of 95%) over the reference product (cure rate 55%) with a power of 80% at 5% level of significance, 30 subjects are needed per treatment group.

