10.4. Efficacy Analyses

Efficacy analyses will be performed on the ITT population, consisting of all subjects who were included and randomized in the study, with available baseline value of the primary endpoint and at least one follow-up visit for the efficacy parameters. All statistical test will be performed at a 5% level of significance.

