10.4.1. Analysis of primary objective

The cure rate (p) corresponds to the proportion of subjects who are cured at day 10 among all subjects that received any treatment at day 0. The aim of the study is to show superiority for the cure rate of the test product versus a predefined limit of 70%.

The following null hypothesis will be tested:

$$H_{0, \text{prim}}: p_T - p_R = 0 \text{ and } H_a: p_T - p_R > 15\%$$

A χ^2 -test of independence will be used to test the null hypothesis.

In case superiority could not be proven, non-inferiority will be tested. According to ICH guideline “Points to consider on switching between superiority and non-inferiority” [17], it is allowed to assess non-inferiority in to the absence of superiority. Prerequisites include:

- predefinition of a non-inferiority margin
- no correction in terms of multiplicity

As non-inferiority margin (δ), a 7.5% worse cure rate is regarded as clinically not relevant. The following null hypothesis will be used: $H_{0, \text{NI}}: p_T - p_R < \delta$, whereby $\delta = -7.5\%$. The lower, 95% confidence interval (CI) of the difference $p_T - p_R$ will be used for the test. If $H_{0, \text{NI}}$ will be rejected, non-inferiority cannot be shown.

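### Section 10.4.1 leaves the error rate for the between-arm claims unstated: directional alternative, non-directional chi-square against zero, and a lower 95% limit with two readings

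*Combined protocol and SAP*

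**What the plan says.** Four statements in the combined protocol and SAP bear on the error rate of the comparison between arms.

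- Section 10.4: "All statistical test will be performed at a 5% level of significance". Sidedness is not given here or in any other efficacy or sample-size section.
- Section 10.4.1, superiority: the null is a zero difference, the alternative is a difference above 15%, and a chi-square "test of independence will be used to test the null hypothesis".
- Section 10.4.1, non-inferiority, tested if superiority is not shown and without multiplicity correction: "a 7.5% worse cure rate is regarded as clinically not relevant", so the margin is -7.5 points. The tool is "The lower, 95% confidence interval (CI) of the difference" between the cure rates.
- Sample size: for 95% against 55% with a 15-point superiority margin, section 10.2 says that "with a power of 80% at 5% level of significance, 30 subjects are needed per treatment group". Section 8.1, with the same rates and margin, says that "a sample size of 35 subjects in each treatment group results in a power of 80" percent.

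**The concern.** A one-sided alternative combined with a 5% level suggests a one-sided 5% test. The named test does not deliver that. A chi-square of independence at 5% leaves about 2.5% in favour of the test product, and it also rejects when the reference is better. It tests against zero although the alternative is set at 15 points. The comma in the non-inferiority criterion leaves it open whether the bound carries 5% or 2.5% error.

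Superiority and non-inferiority form one switching procedure on one difference, so they should rest on one interval at one error rate. If the level is not fixed in advance, a close result can be called either way after the data are seen. The same gap reaches the 70% objective in section 5.1, because a test of that directional claim at 5% also needs its sidedness stated.

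**Working it through.** **Inputs.** Cure rates 95% and 55%, superiority margin 15 points, 80% power, 5% level, 30 per arm (section 10.2); 35 per arm (section 8.1); non-inferiority margin -7.5 points (section 10.4.1).

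**1. The planned size.** Unpooled formula: n = (z_alpha + z_beta)² × [pT(1-pT) + pR(1-pR)] / (pT - pR - 0.15)². The variance sum is 0.0475 + 0.2475 = 0.295, the squared distance is 0.25² = 0.0625, and the ratio is 4.72.
- One-sided 5%: (1.645 + 0.842)² × 4.72 = 29.2, so 30 per arm. This matches section 10.2.
- One-sided 2.5%: (1.960 + 0.842)² × 4.72 = 37.0 (37.05 before rounding), so 38 per arm. No match.

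The 35 in section 8.1 can be reached in more than one way. With pooled variance under the null, one-sided 5% gives 34.3 (35 per arm) and one-sided 2.5% gives 43.9. But adding the margin to the reference rate and comparing 95% with 70% by the pooled formula at two-sided 5% gives 35.06. The 35 therefore does not settle the sidedness.

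**2. Power under each reading.** Power = Φ(0.25/√(0.295/n) - z_alpha).

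| n per arm | one-sided 5% | one-sided 2.5% |
|---|---|---|
| 30 | 81.0% | 71.3% |
| 35 | 86.0% | 77.7% |

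Exact enumeration of all outcomes at 35 per arm, requiring a Newcombe lower limit above 15 points, gives about 84% and 72%.

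**3. Results that flip at 35 per arm.**
- Superiority, 26/35 against 19/35: chi-square 3.05 without continuity correction, p = 0.081. Halved for direction, p = 0.040.
- Non-inferiority, 24/35 against 19/35: difference 5/35 = 14.3 points, Wald standard error 11.5 points. The lower limit is -4.6 with z = 1.645 (passes -7.5) and -8.3 with z = 1.960 (fails). Newcombe gives -4.7 and -8.2.
- The 70% limit, exact binomial test assumed: 30/35 gives one-sided p = 0.027, which passes at 5% and fails at 2.5%.

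**4. How often it matters.** Exact enumeration at 35 per arm, reference rates 55% to 80%, Wald and Newcombe limits:
- False non-inferiority at a true difference of -7.5 points: 4.6-5.7% (one-sided 95% bound) or 2.4-2.9% (two-sided 95% limit).
- Opposite non-inferiority verdicts: about 5-8% of trials with equal cure rates and 11-16% with a true 10-point advantage.
- At the planning rates of 95% and 55%, the readings disagree in 0.6% of trials for the chi-square and 0.04% for non-inferiority (Wald).

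**5. The chi-square against the 15-point alternative.** At a true difference of exactly 15 points and 35 per arm, the two-sided 5% chi-square favours the test product in 25% (70% against 55%), 32% (85% against 70%) and 52% (95% against 80%) of trials. It cannot support a claim of superiority by more than 15 points.

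**The case against.** The best defence is that the ordinary reading is coherent. A chi-square at 5% spends 2.5% in favour of the product, and a lower 95% limit most naturally means the lower end of the usual two-sided interval, also 2.5%. Both steps then agree. That stands, and it rules out three stronger conclusions that a reader might draw.

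- *That superiority runs at 2.5% while the fallback runs at 5%.* This needs the less usual reading of the non-inferiority phrase. The text permits it but does not require it.
- *That the planned size proves a one-sided 5% design.* Only the 30 per arm points that way, and only under the unpooled formula. The documents give no formula, and 35 is nearly reproduced at two-sided 5%.
- *That a result such as 26/35 against 19/35 could be declared superior under the plan.* Section 10.4.1 does not provide for halving the p-value of its named test. As written, that result is not superior. The open wording lies mainly in the non-inferiority step.

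It is also fair that the fallback serves a secondary objective (section 5.2, item c), and that the readings almost never part at the planning rates. But the fallback is used only when superiority has failed, which is when results are close. The ordinary reading also does not fit the 30 per arm in section 10.2, and it leaves a test against zero facing a 15-point alternative.

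**Conclusion.** The point holds in limited form. Sidedness is nowhere stated, the non-inferiority criterion has two readings whose nominal error rates differ by a factor of two, and the usual reading disagrees with the only sample size that identifies a level. The consequence is confined to borderline results, chiefly in the fallback. The correction is cheap and worth making before data are seen.

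The figures assume 35 evaluable subjects per arm, no continuity correction, and Wald or Newcombe limits, since the plan names no interval method. The quoted disagreement ranges hold for reference rates of 55% to 80%; at 90% in both arms the non-inferiority readings part in 9.4% of trials (Wald). The fix takes the 15 points in sections 8.1, 10.2 and 10.4.1 as the claim to be shown, although section 5.2, item b, names no margin.

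**What to change.** In section 10.4.1, replace the chi-square decision and the lower-limit wording with one rule: compute a single two-sided 95% confidence interval for the difference in cure rates by a named method (for example Newcombe). Claim superiority by the stated margin only if its lower limit exceeds 15 points, and non-inferiority if the same limit exceeds -7.5 points. In section 10.4, state two-sided 5% (one-sided 2.5%) for all tests, including the one against 70%.

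The edit is a few sentences, but it has a price in power. With the 15-point bound, power at 35 per arm is about 78% by the unpooled formula and about 72% by exact Newcombe enumeration; at 30 per arm it is 71% by formula. Sections 8.1, 10.1 and 10.2 must then restate the 80%, or the size must rise: 38 per arm by the unpooled formula, 76 subjects instead of 70.

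The alternative is to declare one-sided 5% once and use a two-sided 90% interval at every step. That keeps 86% by formula and about 84% by exact enumeration at 35 per arm, and 81% by formula at 30 (the same Newcombe enumeration at 30 gives about 78%). Its cost is an openly doubled false-positive rate for each claim. Either choice works if it is written down beforehand and the sample-size text names the same level.

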5.2. Secondary objectives

Secondary objectives refer to comparison of the cure rate of test product with those of reference product using the following endpoints:

Secondary efficacy objectives:

- a) To show that the cure rate at the end of day 10 (corrected for re-infestation) for the reference product for all baseline infestations is better than 70%.
- b) To show that the test product has a cure rate superior to that of the reference product.
- c) In case that superiority cannot be shown: to show that the test product is non-inferior to reference product regarding cure rate. A non-inferiority margin of 7.5% will be used.

Further secondary objectives refer to objectives c and d, however evaluated in subgroups or other time points.

- d) Efficacy of the investigational products for head lice for mild and moderate baseline infestations (cure rate at the end of the study day 10, corrected for re-infestation).
- e) Efficacy of the investigational products for head lice for all baseline infestations (cure rate at day 1).
- f) Efficacy of the investigational products for head lice for mild and moderate baseline infestations (cure rate at day 1).

As further secondary objectives, safety and tolerability of test product or reference as well as the acceptance of the investigational products will be evaluated.

Secondary safety objectives;

- g) To evaluate local tolerability by subject: subjective symptoms (burning, paraesthesia, pruritus): 0h, 1h, 24h, 7d and 10d p.a. (descriptive evaluation).
- h) To evaluate global tolerability by the subject and study staff (number of subjects with global tolerability ratings of “very good”, “good”, “moderate”, “poor”, descriptive evaluation) at 10d

after application.

- i) To evaluate skin irritation by study staff (secondary infection, erythema, excoriation) on day 0, 1, 7 and 10.
- j) To evaluate eye irritation by study staff on day 0, 1, 7 and 10.
- k) To evaluate characterization of safety and tolerability of the investigational products considering Adverse Events in the study population.

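### The non-inferiority decision rule in section 10.4.1 is reversed: rejecting the null of inferiority is said to mean that non-inferiority cannot be shown

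*Combined protocol and SAP*

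**What the plan says.** Objective c in section 5.2 is the fallback if superiority over the reference fails: "to show that the test product is non-inferior to reference product regarding cure rate". The same item fixes the margin: "A non-inferiority margin of 7.5% will be used".

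Section 10.4.1 carries this into the analysis. It gives the trigger, "In case superiority could not be proven, non-inferiority will be tested", and justifies the margin by saying that "a 7.5% worse cure rate is regarded as clinically not relevant". The null hypothesis is H0,NI: pT − pR < δ with δ = −7.5%, and the test is to use the lower 95% confidence limit of pT − pR. The step ends with the decision rule: if H0,NI "will be rejected, non-inferiority cannot be shown". Nothing is said about the case where H0,NI is not rejected.

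On the error level, section 10.4 says only "All statistical test will be performed at a 5% level of significance". Neither section says whether the 5% level or the 95% limit is one- or two-sided, and no interval method is named.

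**The concern.** The null describes inferiority beyond the margin. Evidence against it is evidence for non-inferiority, so the written conclusion has the wrong sign. It conflicts with the null itself, with the rationale for the margin and with the purpose of objective c.

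This is the only fallback comparison with the reference on day-10 cure rate across all baseline infestations. Objectives d to f (mild and moderate infestations, and day 1) are introduced as extensions of earlier objectives including c, so they may inherit the same rule.

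Applied literally, every trial that reaches this step with supportive data must be reported as not showing non-inferiority. If the analyst corrects the rule without an amendment, the reported decision departs from the written plan. Section 10.4.1 itself lists predefinition of the margin as a condition for switching from superiority to non-inferiority, so an undocumented repair after unblinding would be hard to defend.

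**Working it through.** **1. Logic.** Under H0,NI, pT − pR < −0.075. It is rejected when the lower confidence limit L of pT − pR exceeds −0.075. The data are then compatible only with a deficit smaller than the margin, which is non-inferiority. The plan attaches the opposite conclusion to this event. The argument does not depend on sample size, sidedness or interval method. Sections 5, 8.1 and 10 contain no other non-inferiority rule that would override the sentence.

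**2. The plan's own design figure.** There is no sample size for non-inferiority. The stated 30 per group (sections 10.1 and 10.2) is for superiority by 15 points at 95% versus 55% with 80% power. It reproduces at one-sided 5%:

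n = (1.645 + 0.842)² × (0.95×0.05 + 0.55×0.45) / (0.40 − 0.15)² = 6.18 × 0.295 / 0.0625 ≈ 29.2, so 30.

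At one-sided 2.5% the result is 38. The reversed sentence does not enter this calculation.

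**3. A result where the rule bites.** Take 35 per arm (section 8.1) and 26/35 versus 19/35 cured.

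- Difference: 7/35 = 0.200.
- Chi-square without correction: 70 × (26×16 − 9×19)² / (45×25×35×35) = 3.05, two-sided p = 0.081 (0.134 with continuity correction). Superiority is not shown.
- Wald standard error: √(0.743×0.257/35 + 0.543×0.457/35) = 0.1120.
- Two-sided 95% CI: 0.200 ± 1.96 × 0.1120, i.e. −0.020 to 0.420. The Newcombe lower limit is −0.024.
- −0.020 > −0.075, so H0,NI is rejected and non-inferiority is supported. The written rule says it cannot be shown.

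**4. How often this happens.** Exact binomial enumeration with 35 per arm and Wald limits (an assumption, since no method is named) gives P(superiority not shown and L > −0.075). Section 10.4.1 pairs a null of zero difference with an alternative above 15%, so both readings of the superiority step are shown. The 75% versus 65% scenario is an assumed smaller effect and is not taken from the documents.

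| Superiority step | Limit for non-inferiority | 95% vs 55% (planning) | 75% vs 65% (assumed) |
|---|---|---|---|
| Chi-square, two-sided 5% | two-sided 95% | 0.9% (2.0% with continuity correction) | 24% |
| Lower limit above 15%, two-sided 95% | two-sided 95% | 22% | 37% |
| Lower limit above 15%, one-sided 95% | one-sided 95% | 14% | 49% |

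**5. Sidedness.** With 22/35 versus 17/35 the difference is 5/35 = 0.143 and the two-sided chi-square p is 0.23, so superiority fails. The standard error is 0.1175.

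- Two-sided 95%: 0.143 − 1.96 × 0.1175 = −0.087, below −0.075.
- One-sided 95%: 0.143 − 1.645 × 0.1175 = −0.050, above −0.075.

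Even under a corrected rule, these data would give opposite verdicts depending on a choice the plan does not make.

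**The case against.** The strongest reply is that the intent can be recovered. The null, the negative sign of δ, the use of the lower limit and objective c all point the same way, and the sentence reads like a misplaced negation. Only the rejection branch is written, so the plan blocks a valid claim but does not expressly license a false one. This is fair, and for that reason no false-positive rate is claimed here. It still leaves the plan's only written decision rule for this claim wrong, to be repaired by someone who may have seen the data.

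Second, the practical effect may be small. At the planning rates with the one test the plan names, the situation arises in about 1% of trials (2% with continuity correction). The larger figures need either the 15% margin reading or an assumed smaller effect. This stands as a limit on the size of the problem. All the frequencies also use 35 per arm, whereas sections 10.1 and 10.2 give 30.

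Third, the example in step 3 fails superiority on the uncorrected test only if that test is two-sided. One-sided, p is 0.081/2 ≈ 0.040 and the fallback would not be reached, although it would be with continuity correction (0.134/2 ≈ 0.067) or against the 15% margin. The condition is right, but a chi-square test of independence at 5% is naturally read as two-sided.

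Fourth, the sidedness and method of the interval are a separate under-specification. Agreed: they are a secondary note, raised here because they belong in the same sentence of the plan.

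**Conclusion.** The concern holds. The non-inferiority rule in section 10.4.1 is wrong as written, and nothing else in the document corrects it. The error is purely logical and rests on no numerical assumption.

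How often it would change a report does rest on assumptions. With 35 per arm and Wald limits, the range at the planning rates runs from about 1% to 22% of trials, depending on how superiority is judged. With a true effect as small as 75% versus 65% it is 24% to 37% with two-sided 95% limits.

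The consequence is confined to the fallback comparison with the reference, and possibly to the objectives in section 5.2 that build on it. The test product's day-10 cure rate against 70% and the sample size are untouched. Because it is the operative rule for a comparative claim, it must be corrected before the data are analysed.

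**What to change.** Replace the hypothesis and rule in section 10.4.1 with:

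- H0,NI: pT − pR ≤ −7.5 percentage points, against Ha: pT − pR > −7.5 percentage points.
- Non-inferiority is shown if H0,NI is rejected, that is, if the lower confidence limit of pT − pR is above −7.5 points. Otherwise it is not shown.

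In the same place, state whether the limit is the lower end of a two-sided 95% interval (one-sided 2.5%) or a one-sided 95% bound, and name the interval method. Say whether the same rule applies to objectives d to f.

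The cost is one or two sentences, made by documented amendment before analysis. Design, data collection and sample size do not change.

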10.5. Safety Analyses

Safety analyses will be performed in the Safety Population, including all enrolled subjects who administered the investigational product, independently of the duration of treatment.

Safety data will be presented in tabular and/or graphical format and summarized descriptively. A comparison of the secondary characteristics of the lice infestation (see chapter 9.4) will be performed along with tabulation of the reported adverse events.

10.6. Statistical software

All statistical analyses will be performed with R-version 3.4.2 (R development core team, 2017).

10.7. Quality control for statistical procedures

The statistical analyses will be conducted in compliance with the ICH E9 Note for Guidance on Statistical Principles for Clinical Trials (CPMP/ICH/363/96, 1998). Quality control will include data check, calculations check, check of tables, listings, and figures. All steps of quality control will be documented with signature of the reviewer and the review date.

11. QUALITY ASSURANCE

Quality assurance includes all activities undertaken during and after a clinical study to verify and control quality. It embraces internal quality control by the staff itself and by independent second persons as well as monitoring and separate auditing activities. All activities will be performed according to written procedures of the CROs and the facilities involved.

To ensure compliance with GCP and all applicable regulatory requirements, the sponsor may conduct a quality assurance audit. Regulatory agencies may also conduct a regulatory inspection of this study. Such

11.2. Study and Site Closure

Upon completion or premature discontinuation of the study, the monitor will conduct site closure activities with the investigator or site staff, as appropriate, in accordance with applicable regulations including GCP, and the sponsor procedures.

In addition, the sponsor reserves the right to temporarily suspend or prematurely discontinue this study at any time for reasons including, but not limited to, safety or ethical issues or severe non-compliance. If the sponsor determines such action is needed, the sponsor will discuss this with the investigator or the head of the medical institution (where applicable), including the reasons for taking such action. When feasible, the sponsor will provide advance notification to the investigator or the head of the medical institution, where applicable, of the impending action prior to it taking effect.

If the study is suspended or prematurely discontinued for safety reasons, the sponsor will promptly inform investigators or the head of the medical institution (where applicable) and the regulatory authorities of the suspension or premature discontinuation of the study and the reason(s) for the action. If required by applicable regulations, the investigator or the head of the medical institution (where applicable) must inform the IRB/IEC promptly and provide the reason for the suspension or premature discontinuation.

11.3. Data Management

The site or a data management partner will provide a file containing all the needed data to the statistician so the appropriate statistical analyses can be performed. Subject data will be entered into case report forms (CRFs). Subject initials will not be transmitted to the sponsor or data management partner. Case Report Forms will be given to the sponsor, while the sites will retain a copy.

